2.4.6.4 Secondary Outcome Measures

Secondary endpoints are the incidence of any non-reassuring FHR patterns during the "silent" period which is the period when the FHR monitor is removed, the patient's abdomen is scrubbed, sterile prep and drape until delivery of the fetus. If there are any non-reassuring FHR patterns (tachycardia, bradycardia, decelerations), maternal vital signs at the time will be noted.

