2. STUDY PROTOCOL

2.1 Background and Significance

Fetal heart rate (FHR) monitoring has become the most widely used assessment of fetal well-being in the peripartum period and the only routinely used method that provides continuous fetal monitoring. Despite a false positive rate for the detection of intrapartum asphyxia leading to cerebral palsy of over 99% [1-3] FHR monitoring continues to be the mainstay of peripartum fetal surveillance. FHR monitoring is routinely available in the operating room, where it is typically reassessed in cases of urgent cesarean delivery for fetal distress since it may direct immediate anesthetic and peripartum management. However, despite the ubiquitous use of FHR monitoring in labor and the typical use of FHR monitoring on arrival to the OR, FHR monitoring is universally stopped once anesthesia has been performed in order to allow abdominal skin preparation and for surgery to proceed. From the moment of anesthesia induction until fetal delivery, no real-time data is available that allows assessment of fetal well-being. A few isolated studies and case reports in the 1970s-1980s examined intraoperative FHR monitoring using scalp-clip electrodes during Cesarean deliveries [4-7]. None of these studies assessed external FHR monitors or current anesthesia techniques. To our knowledge no studies since that time have examined FHR monitoring during Cesarean deliveries using external monitoring or spinal anesthesia.

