2.2 Objective

The first objective of this study is the introduction of intraoperative fetal heart rate (FHR) monitoring as a novel fetal endpoint to be utilized in scheduled and urgent cesarean deliveries, in order to shed important light on the immediate fetal responses to maternal anesthetic and obstetric interventions. This research is intended to demonstrate that intraoperative FHR monitoring is technically feasible, and correlates with other traditional endpoints of immediate neonatal wellbeing (such as umbilical arterial blood gas analysis and Apgar score). Unlike these post-delivery neonatal outcomes, intraoperative FHR monitoring has the potential to serve as a real-time target for optimization of maternal and fetal condition in order to improve immediate neonatal outcome. We will first assess the fetal ECG monitors on a pilot of 15 patients for induction of labor who are not yet in active labor or in pain; the aim being to determine the best placement of the ECG leads. We will then assess the technical feasibility of intraoperative FHR monitoring using both the standard abdominal wall acoustic device used routinely in labor and a series of multiple ECG leads placed over the upper abdominal wall.

CONFIDENTIAL: This document is the intellectual property of [name]. Acceptance of this document constitutes the agreement by the recipient that no unpublished information contained herein will be published or disclosed without prior written approval.

DoCTR

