CONFIDENTIAL: This document is the intellectual property of [name]. Acceptance of this document constitutes the agreement by the recipient that no unpublished information contained herein will be published or disclosed without prior written approval.

Group 2 – Patients for scheduled cesarean section

- a) We will use the acoustic FHR sensor and the fetal ECG sensors.
- b) We will start with 5 patients and determine if we can capture fetal ECG. If this information correlates with the acoustic FHR, we then use only the fetal ECG sensors for the remaining 35 patients. We will adjust placement of leads for each group of 5 patient if there proves to be difficulty with capturing FHR intraoperatively, though all leads will be placed on the belly outside the sterile field or on the participant's back
- c) We will plan for an upper limit of 40 patients in this group

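### No pre-spinal fetal heart rate segment is specified or analysed in Group 2, so the silent-period incidence cannot be read as a response to anesthesia

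*Combined protocol and SAP*

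**What the plan says.** Section 2.4.6.4 defines the secondary endpoint as the incidence of non-reassuring patterns (tachycardia, bradycardia, decelerations) in the silent period, "which is the period when the FHR monitor is removed". The window then runs through skin preparation and draping and closes at delivery. Maternal vital signs are to be noted when a pattern occurs.

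Section 2.1 fixes where that window sits relative to the spinal: "FHR monitoring is universally stopped once anesthesia has been performed in order to allow abdominal skin preparation and for surgery to proceed". The same section describes the gap in knowledge as starting earlier: "From the moment of anesthesia induction until fetal delivery, no real-time data is available that allows assessment of fetal well-being".

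Section 2.2 introduces intraoperative monitoring as a new fetal endpoint "in order to shed important light on the immediate fetal responses to maternal anesthetic and obstetric interventions". It then says what the present work should show: "This research is intended to demonstrate that intraoperative FHR monitoring is technically feasible, and correlates with other traditional endpoints of immediate neonatal wellbeing".

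For the cesarean patients (Group 2), section 2.4.6 says "We will use the acoustic FHR sensor and the fetal ECG sensors". It gives no time at which either recording starts and names no reference segment. If the two devices agree in the first 5 patients, only the ECG is used in the remaining 35. Section 2.4.6.5 plans descriptive statistics for demographic and clinical characteristics and an ROC comparison of the two devices. It plans no before/after summary.

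**The concern.** Every Group 2 patient has spinal anesthesia (section 2.3.1), so the study has no concurrent comparator. The only available reference for a response is the same fetus before the spinal, and the plan does not make that segment study data.

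Two things follow. A bradycardia or deceleration seen in the silent period cannot be told apart from one already present on arrival. A pattern that begins after the spinal and resolves before the routine monitor comes off is not counted at all.

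This matters because the protocol invites a causal reading. Section 2.2 speaks of responses to interventions, section 2.4.6.4 links patterns to maternal vital signs, and section 3.4 mentions a possible change in anesthetic management as a benefit of the study series. A bare incidence supports none of these. A reference not kept before delivery cannot be recovered afterwards.

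**Working it through.** **The plan's own figure.** The only number to reproduce is the sample size in section 2.4.6.6: 15 + 40 = 55. It is the sum of the two group limits. No expected incidence, precision target or effect size is given, so every rate below is an assumption.

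**The windows, set side by side.**

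| Period in Group 2 | Counted in the secondary endpoint? | Named as study data or analysed separately? |
|---|---|---|
| Before the spinal | No | No |
| Spinal to monitor removal | No | No |
| Monitor removal to delivery | Yes | Yes, as one incidence |

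The only FHR recording with a set length is the 10 minutes in Group 1. Those are different women, having induction, so it cannot serve as a within-fetus baseline.

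**What a one-window count can show.** Take n = 40 (the Group 2 limit) and an assumed x = 8 patients with a pattern: 8/40 = 20%. The exact (Clopper-Pearson) 95% limits are:

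- lower = 0.025 quantile of Beta(x, n − x + 1) = Beta(8, 33): 9.1%
- upper = 0.975 quantile of Beta(x + 1, n − x) = Beta(9, 32): 35.6%

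That interval covers sampling error only. The net change is the silent-period rate minus the pre-spinal rate, and the second term is not measured:

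| Assumed pre-spinal rate | Expected patients in 40 | Net rise if 20% is seen later |
|---|---|---|
| 0% | 0 | 20 points |
| 5% | 40 × 0.05 = 2 | 15 points |
| 15% | 40 × 0.15 = 6 | 5 points |
| 20% | 40 × 0.20 = 8 | 0 points |

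The plan reports 8/40 in every row. More patients would narrow the interval but would not identify the row.

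**Why a baseline needs adjustment for time.** Suppose patterns start at a constant rate and 10% of fetuses (the midpoint of 5% and 15%) show one in a baseline window. In a silent period twice as long, with no response to anything, the expected proportion is 1 − (1 − 0.10)² = 1 − 0.81 = 19%. A longer window alone could thus produce almost the whole of an apparent 20%. The documents do not state the length of the silent period, so raw incidences from different windows should not be compared.

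**What 40 pairs could support.** Exact two-sided McNemar power at the 5% level, n = 40, for assumed discordant proportions:

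| Pattern only after / only before | Power |
|---|---|
| 10% / 2.5% | 0.10 |
| 15% / 2.5% | 0.32 |
| 20% / 2.5% | 0.57 |
| 20% / 5% | 0.36 |
| 25% / 5% | 0.57 |
| 30% / 5% | 0.74 |

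A baseline makes within-fetus change estimable, but these figures argue for describing it rather than testing it.

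**The case against.** The strongest reply is that this is a feasibility study. Sections 2.2, 2.4 and 2.4.6.3 put technical feasibility, sensor performance and correlation first. The clause on fetal responses concerns an endpoint for scheduled and urgent cesareans, yet section 2.3.2 excludes urgent ones, so it reads as the eventual use of the method. Describing how often patterns occur while the routine monitor is off is a coherent secondary endpoint and does not itself claim causation. This stands. A reader might infer that the study fails its objective; the documents do not support that.

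A reader might also infer that no pre-spinal recording will exist. The documents do not say so. Section 2.4.6 is silent on start times, section 2.1 calls monitoring on arrival in the operating room typical, section 2.4.6.4 presupposes a monitor that is later removed, and section 3.2 lists fetal heart rate among data from the electronic record. A routine trace may well cover both uncounted periods. The gap is that no section specifies, extracts or analyses it. If it is acoustic and the later trace is ECG, as planned for up to 35 of the 40 patients, device and period are also confounded.

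Three further points stand. The interval from spinal to monitor removal has no stated length and may be short. A before/after change still mixes anesthesia with positioning, preparation and surgery. And leads on the back, which section 2.4.6 allows, may conflict with placing the spinal.

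**Conclusion.** The point holds in a limited form. No same-fetus pre-spinal segment is specified or analysed in Group 2, so the silent-period incidence cannot distinguish a new pattern from an existing one and should not be reported as a response to anesthesia. With an assumed 8 of 40, the number of new patterns could be anything from 0 to 8. That range follows from the missing reference and does not depend on signal quality or sample size.

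The conclusion rests on section 2.1's statement that monitoring stops after anesthesia, and on the absence of any baseline segment or before/after summary in sections 2.4.6 to 2.4.6.5. It touches a descriptive secondary endpoint and the wording of the objective, and leaves the primary endpoint intact. It is a low-cost improvement, not a fatal flaw.

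**What to change.** In Group 2:

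1. Keep as study data the routine acoustic trace from arrival in the operating room to monitor removal. Start the fetal ECG before the spinal where lead position allows; back leads may have to wait. Do not delay surgery for this, consistent with section 2.5.
2. Time-stamp spinal injection, monitor removal or start of preparation, incision and delivery.
3. Describe patterns for three periods (pre-spinal, spinal to removal, removal to delivery) per minute of readable signal, naming the device used in each. Show how many silent-period patterns were absent before the spinal. Keep the existing incidence as one row.
4. State that any before/after change is descriptive and cannot isolate anesthesia from positioning, preparation and surgery.

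If no baseline is kept, limit the wording of section 2.2 to feasibility and present the silent-period incidence without reference to responses.

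The cost is protocol wording, four time stamps, slightly earlier set-up, re-checking of leads after positioning, and some missing baselines. The 30-minute early arrival in section 3.3 should not be counted as spare recording time: it is for admission and consent, and patients approached on the day do not have it.

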2.4.6.5 Statistical Methods

Demographic and clinical characteristics will be summarized using descriptive statistics; FHR data will be compared for the two tests using Receiver Operating Characteristic or ROC curve.

[figure not shown]

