2.4.6 Observations and Measurements

This will be an observational study. We will first assess the fetal ECG monitors on a pilot group of patients for induction of labor who are not yet in active labor or in pain. We will then assess the technical feasibility of intraoperative FHR monitoring. Fetal heart rate will be assessed by:

a) External abdominal wall fetal ECG sensors placed at the top of the belly, outside the sterile field, or on the participant's back. This data is captured via BioSemi FLAT Active electrodes that interface with an ECG system that employs the algorithm ActiView to analyze the data. [See Appendix A].

[figure not shown]
b) An acoustic fetal heart sensor, as used routinely in labor will be used as a comparator in this feasibility study. When this device is used intraoperatively, sterility and acoustic contact are both maintained by placing the acoustic probe inside a sterile nylon sleeve containing electrode gel, and by using sterile electrode gel between the sterile sleeve and the abdominal wall. This technique may require the presence of an investigator "scrubbed into" the case to hold the abdominal wall probe (ie surgical scrub, sterile gown and gloves). This will be decided on a case-by-case basis. If needed, this investigator will need acoustic input to ensure adequate contact. So as not to distract the surgeon, this will be transmitted to the investigator by earphone input. These are scheduled cesarean deliveries and no fetal heart rate anomalies are expected; if there is an unexpected fetal bradycardia, this will be communicated to the surgeon.

c) Routine maternal vital signs (heart rate, blood pressure and oxygen saturation).

Group 1 – Patients for elective induction – not in active labor

- a) We will use the routine acoustic fetal heart rate sensor and try to determine the best placement of external abdominal wall fetal ECG sensors (either at the top of the belly outside the sterile field, or on the participant's back)
- b) We aim to capture 10 minutes of FHR with the ECG sensors comparing it to the acoustic monitor
- c) We will start with 5 patients. If we are able to capture FHR for the allotted period of time with the fetal ECG, then we will proceed to the intraoperative group. If not, we will assess another 5 elective induction patients.
- d) We will plan for an upper limit of 15 patients in this group

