2.4.6.3 Primary Outcome Measures

The primary endpoint of the feasibility study is the use of external abdominal wall fetal ECG sensors to assess FHR; its use-friendliness, the signal-noise ratio and the correlation with acoustic data.

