3.2 Sources of Materials

[figure not shown]
The source of data for the study will come from the patient's electronic record. This information includes fetal heart rate, patient blood pressure, dose of vasopressor, patient cardiac output, fetal blood gases.

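### The rule for dropping the acoustic sensor, the primary endpoint and the ROC comparison all rest on measures that ignore a constant offset, so they cannot show whether the two monitors read the same fetal heart rate

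*Combined protocol and SAP*

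**What the plan says.** The acoustic sensor is the comparator for the fetal ECG, so both devices give a rate in bpm for the same fetus. The plan compares them in four places.

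- **Section 2.4.6, Group 1:** "We aim to capture 10 minutes of FHR with the ECG sensors comparing it to the acoustic monitor". No method of comparison is named. Recruitment goes in steps of 5, up to 15 patients.
- **Section 2.4.6, Group 2:** after the first 5 cesarean patients, "If this information correlates with the acoustic FHR, we then use only the fetal ECG sensors for the remaining 35 patients". No coefficient, threshold or bpm tolerance is given.
- **Section 2.4.6.3:** the primary endpoint covers ease of use, "the signal-noise ratio and the correlation with acoustic data".
- **Section 2.4.6.5:** apart from descriptive statistics, the only method is "FHR data will be compared for the two tests using Receiver Operating Characteristic or ROC curve".

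No section plans a mean difference, limits of agreement, a tolerance in bpm, or sensitivity and specificity at a stated cut-off.

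**The concern.** Whether a new monitor can stand in for an established one is a question of agreement: do the two give the same number, to within a tolerable difference? Correlation asks whether the readings rise and fall together. An ROC curve asks whether one reading ranks cases above non-cases. A device can do well on both and still be consistently wrong in bpm.

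The ROC analysis also lacks a binary reference. The documents offer two candidates, and section 2.4.6.5 links to neither.

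- **The secondary-endpoint patterns:** "If there are any non-reassuring FHR patterns (tachycardia, bradycardia, decelerations), maternal vital signs at the time will be noted". They carry no bpm cut-offs, and for the scheduled cesareans the plan says "These are scheduled cesarean deliveries and no fetal heart rate anomalies are expected".
- **Neonatal outcomes:** section 2.2 intends to show that intraoperative monitoring "correlates with other traditional endpoints of immediate neonatal wellbeing (such as umbilical arterial blood gas analysis and Apgar score"), and section 3.2 lists blood gases among the data ("This information includes fetal heart rate, patient blood pressure, dose of vasopressor, patient cardiac output, fetal blood gases"). On this reading the curve would compare prediction, not agreement. If the Group 2 rule is met, only 5 cesarean patients would have both monitors.

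The Group 2 rule carries the most weight. Once it is met, 35 of the 40 cesarean patients have ECG alone. Tachycardia and bradycardia in the secondary endpoint depend on the absolute rate. An offset that passed the rule would carry into that endpoint, with no paired acoustic record in those patients to reveal it.

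**Working it through.** **Counts from the documents.** Group 2 is 5 + 35 = 40, and the total is 15 + 40 = 55. No SD, margin or precision target is stated, so there is no statistical derivation to reproduce. If the Group 2 rule is met after its first 5 patients, those with both monitors number 5 + 5 = 10 to 15 + 5 = 20.

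**Invariance (no assumptions).** For any constant c, Corr(X + c, Y) = Corr(X, Y). Adding c leaves every ranking unchanged, so the ROC curve and its area stay the same; only the bpm value attached to each point on the curve moves.

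**Size (all inputs assumed, since the documents give none).** Reference rate T ~ N(135, 12) bpm; device error e ~ N(0, 5); reference state T < 110; illustrative tolerance 10 bpm. r and the percentages follow from the normal model; ROC areas come from 2,000,000 simulated pairs.

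- Unbiased device T + e: r = 12/√(12² + 5²) = 12/13 = 0.92. Within 10 bpm: P(|Z| < 10/5) = 95%. Limits of agreement: 0 ± 1.96 × 5 = −9.8 to +9.8.
- Device 20 bpm high, T + e + 20: r is again 12/13. Within 10 bpm: P(−30 < e < −10) = 2%. Limits: 20 ± 9.8 = +10.2 to +29.8.
- Half-rate device with the same error, 0.5T + e: r = 6/√(36 + 25) = 0.77. Mean difference −67.5 bpm.
- Half-rate device with the error also halved, 0.5(T + e): r = 0.92.

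| Device | r | ROC area | Pairs within 10 bpm |
|---|---|---|---|
| Unbiased | 0.92 | 0.989 | 95% |
| +20 bpm | 0.92 | 0.989 | 2% |
| Half rate, same error | 0.77 | 0.95 | 0% |
| Half rate, error halved | 0.92 | 0.989 | 0% |

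For reference SD 8 to 16 and error SD 3 to 10, r runs from 8/√164 = 0.62 to 0.98 and the area from 0.95 to 1.00. At each setting both are identical for the unbiased and +20 bpm devices. The share within 10 bpm depends only on the error SD: as that rises from 3 to 10, it goes from 99.9% to 68% for the unbiased device and from 0.04% to 16% for the +20 bpm device.

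**Fixed cut-off.** Calling a reading positive when the device shows < 110, sensitivity is 0.75 for the unbiased device and 0.015 for the +20 bpm device. A stated cut-off would therefore expose the offset, but none is stated.

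**Events for an ROC curve.** P(T < 110) = Φ(−25/12) = 1.9% of readings. With one reading in each of 5 patients, the chance of any positive is 1 − 0.981⁵ = about 9%, so in most such samples no curve could be drawn.

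**Which rule for Group 2?** A rule on the mean difference alone (within 10 bpm; 5 patients, one pair each) has its own blind spot. A device unrelated to the fetus, N(135, 12), has difference SD 12√2 = 17.0 and SD of the mean 17.0/√5 = 7.6, and passes with P(|Z| < 10/7.6) = 81%. A device stuck at 135 passes with P(|Z| < 10/(12/√5)) = 94%. The percentage of pairs within the limit reacts to offset and scatter together: 44% for the unrelated device and 60% for the stuck one, against 95% for the unbiased one.

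**Precision.** With one pair per patient, the 95% CI half-width of each limit of agreement, in SDs of the differences, is t × √(1/n + 1.96²/(2(n − 1))).

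- n = 5: 2.776 × √(0.200 + 0.480) = 2.29
- n = 10: 2.262 × √(0.100 + 0.213) = 1.27
- n = 20: 2.093 × √(0.050 + 0.101) = 0.81

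**The case against.** **The study tests feasibility, and correlation may be meant loosely as matching.** This is a fair reading. But the word recurs in the primary endpoint, no section gives a criterion for either meaning, and the Group 2 rule changes what data are collected.

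**The plan names the ROC curve, not its area, and sets no pass mark.** This stands: nothing in section 2.4.6.5 passes or fails a device. The whole curve is equally unaffected by an offset, and the missing reference state remains the plainer defect.

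**Real faults may not be a constant offset.** This also stands. A half-rate device with unchanged error lowers r to 0.77. Offsets that differ between patients also lower pooled r: under other assumed inputs (mean 140, SD 15, error SD 3 on each device), between-patient offset SDs of 5, 10 and 20 bpm gave r of 0.92, 0.81 and 0.53. A lower r still does not state the disagreement in bpm.

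**Five patients are too few for an agreement analysis.** They can screen for gross disagreement only, and the fix must say so. Group 1 adds 5 to 15 paired patients before that point, though not under operating conditions.

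**Conclusion.** Wrong as written. The stated comparisons of the two monitors cannot show that they read the same rate. The invariance is algebra; the sizes (95% against 2% of pairs within 10 bpm, at equal r and equal ROC area) rest on the assumed mean, SDs, offset and tolerance.

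The Group 2 rule should be changed before the first cesarean patient is assessed under it. The endpoint wording and the ROC sentence can still be corrected on stored data where both monitors were recorded.

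A reader might infer more than the documents support:

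- **That the planned measures would miss any faulty device.** They miss a common offset, or signal and error rescaled together, and not every fault.
- **That the ECG system is biased.** Nothing in the documents suggests it; the 20 bpm offset is an illustration.
- **That the whole primary endpoint fails.** Ease of use and signal-noise ratio are not affected.
- **That only 5 patients would be paired.** With Group 1 the total is 10 to 20 if the rule is met after the first 5 cesarean patients. The loss of 35 acoustic recordings follows only if it is met.

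**What to change.** **Section 2.4.6, Group 2 (first).** Replace the correlation condition with one named rule: *at least a pre-set percentage of time-matched pairs in the first 5 cesarean patients lie within a pre-set bpm limit*. Report bias and limits of agreement alongside. The investigators must set the limit and the percentage, because the documents give neither; 10 bpm above is only illustrative. Add that 5 patients screen for gross disagreement only, with each limit known to about ±2.3 SD. Report the 5 to 15 paired Group 1 patients separately, as supporting data.

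**Section 2.4.6.5.** Replace the ROC sentence with: *Time-matched paired FHR values will be compared by Bland-Altman bias and 95% limits of agreement, with a repeated-measures variance (random patient effect) and patient-level confidence intervals, plus the percentage of pairs within a bpm limit fixed before data are seen.* Keep ROC as exploratory only if reference events occur and the reference state, cut-off and unit of analysis are defined.

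**Section 2.4.6.3.** Change correlation to agreement.

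**Cost.** Wording in three sections and no extra patients. There is one operational change: section 3.2 takes fetal heart rate from the electronic record and section 3.2.2 describes only the ECG capture, so the acoustic trace must be exported and time-matched to the ECG. Several readings per patient sharpen the within-patient part of the variance but not the between-patient part, so the limits stay imprecise with 10 to 20 paired patients (about ±1.3 to ±0.8 SD with one pair each).
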